	2.) Arm 2: Placebo Controls (n = 6) . These subjects will be treated with identically appearing placebo i.v. on the same schedule as the experimental arm subjects (i.e., three "loading" doses, two weeks apart, followed by five more monthly infusions. Again, the final assessment will be performed at month 7 ($210+10$ days after treatment start).
Planned Sample Size:	A total of 18 subjects will be enrolled in this trial. In order to reach the needed sample size of 18, twenty-five subjects will be randomized to account for subjects who have been withdrawn early due to the current COVID-19 pandemic in order to comply with guidance regarding human subjects research conduct and also for medical reasons un-related to study drug or study procedures.
Duration of Treatment:	Six months
Duration of Participation	Ten months
Inclusion Criteria:	 A history of past tobacco smoking (≥10 pack years), but quit for ≥6 months at the time of enrollment. Smoking cessation will be confirmed by serum cotinine assays.
	2.) Clinical diagnosis of at least moderate COPD as defined by the Global Initiative for Obstructive Lung Disease (GOLD) criteria:

	 a. Post bronchodilator FEV₁/FVC < 70%, b. Post bronchodilator FEV₁ between 25% and 80% predicted, with or without chronic symptoms (i.e., cough, sputum production). COPD
	3.) Ability and willingness to give informed consent.
	4.) Levels of plasma autoantibodies against a 15–mer peptide sequence within the GRP78 molecule (a.a. 246-260) that are in the upper three quartiles of values present in COPD patients. This epitope will henceforth be denoted as GRP78 Peptide 25. Levels of anti-GRP78 Peptide 25 autoantibodies are significantly correlated with carotid artery intimal medial thickness (IMT) among COPDpatients.
	5.) Age 40-75 y.o. COPD is a disease of older individuals.
Major Exclusion Criteria:	1.) History of more than one moderate (treated as outpatient) or severe (requiring hospitalization) acute exacerbation of COPD within the 12 months prior to screening or any moderate or severe exacerbation within the 4 months prior to screening. A past history of an acute exacerbation is the single biggest risk for recurrence. ³⁶ Exclusion of subjects at highest risk will minimize dropouts.
	2.) Oral steroids or cellular immunosuppressant use (e.g., cyclophosphamide) within 6 months.
	3.) History or clinical or laboratory evidence of other autoimmune syndromes (confirmed by self-report and medical record review).

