Our subject numbers are small, and this will limit our power to detect small intergroup differences, especially if there are biological differences of drug actions within our demographically and ethnically heterogeneous study population. This problem(s) will be confounded if there are several subject drop-outs due to the development of acute exacerbations, or if they lose interest and quit participating.

We have attempted to minimize the potential number of acute exacerbation drop-outs by excluding those patients with the single greatest risk for these complications (i.e., those who have a history of same). And the UAB LHC has a very good record for retaining trial subjects (approaching 100% in several studies). Furthermore, our data analysis methods should still enable us to make meaningful intergroup comparisons if there are subject drop-outs (see **Data Analyses**).

The alternative would be to propose a much bigger and more expensive initial trial, in the face of having absolutely no prior experience in COPD patients with this particular agent, or even this general approach. However, this would expose many more subjects to potential risks of the experimental intervention, prior to having any indication of effectiveness or safety.

The effectiveness of belimumab in autoimmune COPD patients is currently unknown, and it is conceivable that the autoimmune responses in this lung disease population are actually more fulminant, or otherwise more refractory, than those of SLE patients. Of course, a rationale for the

proposed study is to begin to explore this possibility. If, for whatever reason(s) COPD autoimmunity is resistant or partially resistant, it will further hinder our ability to find a treatment effect. Based on results of clinical trial results in other disease populations, and general biological considerations,^{23,33,34,37} we are confident that belimumab will, in fact, detectibly reduce anti-GRP78 IgG in the treatment arm, and will likely alter circulating B-cell populations as well, even given the inherent limitations of this trial.

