3.2 INCLUSION AND EXCLUSION CRITERIA

The inclusion criteria have been selected to study a patient population with COPD and autoimmunity. The exclusion criteria are selected to exclude patients with increased risk for the experimental intervention.

Inclusion Criteria

1.) A history of past tobacco smoking (\geq 10 pack years), but quit for \geq 6 months at the time of enrollment. Smoking cessation will be confirmed by serum cotinine assays.

2.) Clinical diagnosis of at least moderate COPD as defined by the Global Initiative for Obstructive Lung Disease (GOLD) criteria:

- a. Post bronchodilator FEV₁/FVC < 70%,
- b. Post bronchodilator FEV₁ between 25% and 80% predicted, with or without chronic symptoms (i.e., cough, sputum production).

COPD

3.) Ability and willingness to give informed consent.

4.) Levels of plasma autoantibodies that have specifities against a 15–mer peptide sequence within the GRP78 molecule (aa. 246-260) that are in the upper three quartiles of values present in COPD patients. We have discovered that circulating levels of IgG autoantibodies with avidity against this peptide (GRP78 Peptide 25) are associated with the magnitude of carotid artery intimal medial thickness (IMT) among COPD patients (Figure 5). Limiting enrollments to subjects with readily detectible autoantibodies (e.g., those with levels in the 25th percentile or above) will easily enable us to ascertain if the experimental treatment (belimumab) results in a significant reduction of these autoantibodies.

5.) Age 40-75 y.o. COPD is a disease of older individuals.

Exclusion Criteria

1.) History of prior acute COPD exacerbations or no more than one moderate exacerbation in the last year and no exacerbations four months prior to enrollment. A past history of an acute exacerbation is the single biggest risk for recurrence.³⁶ Exclusion of these higher-risk subjects will minimize drop-outs.

2.) Oral steroids or cellular immunosuppressant use (e.g., cyclophosphamide) within 6 months.

3.) History or clinical or laboratory evidence of other autoimmune syndromes.

4.) Inability or unwillingness to complete the treatment and surveillance protocols.

5.) Eligible for lung transplant at time of enrollment. This exclusion will mitigate any potential, however slight, that a patient could be rejected for transplantation due to surgeon concerns about this novel therapy (and will also obviate early drop-outs due to transplantation).

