6.) History of malignant neoplasm within the last 5 years.

7.) Evidence of serious suicide risk including any history of suicidal behavior in the last 6 months and/or any suicidal ideation in the last 2 months or those, in the investigator's judgment, pose a significant suicide risk.

8.) History of a primary immunodeficiency.

9.) Significant IgG deficiency (IgG level < 400 mg/dL).

10.) Have an IgA deficiency (IgA level < 10 mg/dL).

11.) Currently on any suppressive therapy for a chronic infection (such as tuberculosis, pneumocystis, cytomegalovirus, herpes simplex virus, herpes zoster or atypical mycobacteria).

12.) Hospitalization for treatment of infection within 60 days of screening.

13.) Use of parenteral (IV or IM) antibiotics (antibacterials, antivirals, anti-fungals, or anti-parasitic agents) within 60 days of screening.

14.) Current drug or alcohol abuse or dependence, or a history of drug or alcohol abuse or dependence within 365 days prior to screening.

15.) History of a positive HIV test or positive screening test for HIV.

16.) Serologic evidence of current or past Hepatitis B (HB) or Hepatitis C (HC) infection based on positive tests for HBsAg or HBcAb, or HCAb.

17.) History of an anaphylactic reaction to parenteral administration of contrast agents, human or murine proteins or monoclonal antibodies.

18.) Any other clinically significant abnormal laboratory value in the opinion of the investigator.

19.) Any intercurrent significant medical or psychiatric illness that the investigator considers would make the candidate unsuitable for the study.

20.) Women of Child Bearing Potential (WCBP) must have a negative urine pregnancy test at screening, and agree to 1 of the following:

Complete abstinence from intercourse from 2 weeks prior to administration of the 1st dose of study agent until 16 weeks after the last dose of study agent (Sexual inactivity by abstinence must be consistent with the preferred and usual lifestyle of the subject. Periodic abstinence (e.g. calendar, ovulation, symptothermal, post-ovulation methods) and withdrawal are not acceptable methods of contraception)

OR

Consistent and correct use of 1 of the following acceptable methods of birth control for 1 month prior to the start of the study agent, during the study, and 16 weeks after the last dose of study agent:

- Oral contraceptive, either combined or progestogen alone
- Injectable progestogen
- Implants of levonorgestrel or etonogestrel

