5.6.3 Adverse Events Reporting Timeline

The investigators or site staff are responsible for detecting, documenting and reporting events that meet the definition of an AE or SAE. AEs will be collected from the start of study treatment and until the follow up contact. SAEs will be collected over the same time period as stated above for AEs. However, any SAEs assessed **as related** to study participation (e.g., study treatment, protocol-mandated procedures, invasive tests, or change in existing therapy) or related to a GSK concomitant medication, will be recorded from the time a subject consents to participate in the study up to and including any follow up contact.

The investigators will report life-threatening or fatal unexpected adverse events associated with the use of the study drug or procedures to the DSMB, and the IRB within 24 hours of discovery of the incident with subsequent follow-up submission of a detailed written report.

All SAE will be reported via email notification within 24 hours of awareness to the following sponsor (GSK) contacts including:

- 1) ISS Chairperson
- 2) ISS Managing Director
- 3) GMAL or designee
- 4) LOC Physician
- 5) LOC Safety Contact
- 6) LOC Study Accountable Person
- 7) GCSP Safety Physician
- 8) GCSP Safety Scientist
- 9) [contact]

Serious (but not fatal or life-threatening) and unexpected adverse events associated with the use of the study drugs or procedures must be reported to the DSMB and the IRB within 5 working days with subsequent follow-up submission of a detailed written report.

Adverse Events of Special Interest:

The following adverse events of special interest will be assessed for frequency in the data analyses and final report.

- Serious Hypersensitivity or Infusion Reactions
- Serious infections, including herpes zoster and opportunistic infections
- Malignancy
- Suicidal thought, intent or behaviour

5.6.4 Stopping Rules:

Individual subject-specific stopping rules: A study participant will be discontinued from further study drug treatment/Intervention(s) administration if any of the following occur:

Any clinical adverse event, laboratory abnormality, intercurrent illness, other medical condition or situation occurs such that continued participation in the study would not be in the best interest of the participant.

An unexpected fatal or life-threatening adverse event, which requires discontinuation of study treatment.

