Patients who develop acute exacerbations that require an addition to their lung medications, or a hospitalization, will be terminated from the study. Any subject who develops new conditions or statuses that would have been an exclusion criterion, will be terminated from the trial.

Request by the subject to withdraw from the study.

Specific Liver Chemistry Stopping Criteria:

Liver chemistry stopping and increased monitoring criteria have been designed to assure subject safety and evaluate liver event etiology (in alignment with the FDA premarketing clinical liver safety guidance).

- ALT Absolute: $ALT \ge 8x$ upper limit of normal (ULN)
- ALT Increase:
 - \circ ALT \geq 5xULN but <8xULN persists for \geq 2 weeks
 - ALT \ge 3xULN but <5xULN persists for \ge 4 weeks
- Bilirubin: ALT \ge 3xULN and bilirubin \ge 2xULN (>35% direct bilirubin)

All events of ALT \ge 3xULN and bilirubin \ge 2xULN (>35% direct bilirubin) or ALT \ge 3xULN and INR>1.5, if INR measured which may indicate severe liver injury (possible 'Hy's Law'), must be reported as an SAE (excluding studies of hepatic impairment or cirrhosis); INR measurement is not required and the threshold value stated will not apply to subjects receiving anticoagulants.

- INR: ALT \geq 3xULN and INR>1.5, if INR measured
- Cannot Monitor:
 - \circ \quad ALT \geq 5xULN but <8xULN and labs cannot be monitored weekly for $\geq\!\!2$ weeks

- ALT ≥ 3xULN but <5xULN and labs cannot be monitored weekly for ≥4 weeks
- Symptomatic: ALT ≥ 3xULN associated with symptoms (new or worsening) believed to be related to liver injury or hypersensitivity
 - New or worsening symptoms believed to be related to liver injury (such as fatigue, nausea, vomiting, right upper quadrant pain or tenderness, or jaundice) or believed to be related to hypersensitivity (such as fever, rash or eosinophilia)

Required Actions, Monitoring, and Follow up Assessments following ANY Liver Stopping Event Actions:

The study treatment will be Immediately discontinued

The event will be reported to GSK within 24 hours

Liver event follow up assessments will be performed (as stated below)

The subject will be monitored until liver chemistries resolve, stabilize, or return to within baseline (see MONITORING below)

Treatment will not be restarted or rechallenged in the subject

Monitoring:

For bilirubin or INR criteria:

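### Two stopping rules take subjects out of the trial, not just off study drug, and no endpoint samples are planned for them afterwards

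*Combined protocol and SAP*

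**What the plan says.** Section 5.6.4 opens its subject-level rules with "A study participant will be discontinued from further study drug treatment/Intervention(s) administration if any of the following occur". Two later sentences in the same list go further. For exacerbations: "Patients who develop acute exacerbations that require an addition to their lung medications, or a hospitalization, will be terminated from the study". For exclusion criteria: "Any subject who develops new conditions or statuses that would have been an exclusion criterion, will be terminated from the trial". The liver chemistry rules in that section, by contrast, stop treatment and prescribe follow-up without ending participation.

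The exclusion list in Section 3.2 includes "Oral steroids or cellular immunosuppressant use (e.g., cyclophosphamide) within 6 months", "Hospitalization for treatment of infection within 60 days of screening" and an IgG level below 400 mg/dL. Several entries are timed from screening, so applying them to events during treatment takes some interpretation. The second sentence nevertheless asks for it.

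Endpoint blood is drawn before treatment and on days 30, 90, 150 and 210 (Sections 2.6.4, 2.7.1 and 2.7.2; Table 2). Section 2.8.1 specifies repeated-measures mixed models. It also specifies intention to treat, with each subject's last observed value as the primary measure. It expects the autoantibody effect by about six months of therapy or later. Section 2.9.1 counts exacerbations as a source of loss: "This problem(s) will be confounded if there are several subject drop-outs due to the development of acute exacerbations".

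**The concern.** An intention-to-treat analysis needs outcomes for everyone randomised, including those who stop treatment. Here the protocol itself ends participation, and with it the endpoint data, after events that need not be independent of disease or treatment.

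- **Disease.** An exacerbation marks worsening lung disease, and Section 2.7.1 reports that anti-GRP78 optical density tended to rise as lung disease worsened. The trigger for leaving may therefore be linked to the primary endpoint.
- **Treatment.** Infection and falling IgG could plausibly relate to a drug that acts on B cells. Section 2.9.1 treats infection risk as a particular consideration in this population.

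At stake are the late values of the primary endpoint. The two laboratory secondary endpoints are affected too, in the subjects with infections or exacerbations for whom host-defence antibody data matter most.

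**Working it through.** This is mainly a check of the text, with a count of samples.

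**1. Do the two sentences end participation or only drug?** The lead-in and the liver rules are worded as stopping drug. The two sentences are worded as leaving the study or the trial, and Section 2.9.1 refers to exacerbation drop-outs. The section is inconsistent, but the operative sentences, read as written, end participation.

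**2. Does any section restore endpoint sampling?** Three kinds of follow-up after removal are described:

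- Section 2.6: adverse events that led to removal are followed until they resolve or stabilise.
- Section 5.6.2: the clinical course of adverse events is followed.
- Section 5.6.4: liver chemistries are monitored after a liver stopping event.

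All three are safety follow-up. None includes an endpoint draw, and there is no early-termination visit. No sentence forbids sampling either; the plan is silent.

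**3. How many samples are lost?** There are four post-baseline draws (days 30, 90, 150, 210):

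| Termination | Draws lost | Last endpoint value available |
|---|---|---|
| before the day 30 draw | 4 | pre-treatment |
| after day 30, before day 90 | 3 | day 30 |
| after day 90, before day 150 | 2 | day 90 |
| after day 150, before day 210 | 1 | day 150 |

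The last infusion is on day 180, so day 210 is the only endpoint draw after the full six-month course. In the first row the last observed value is the baseline itself, so the recorded change is zero by construction. This rule applies in both arms.

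**4. What does the analysis do with the gap?** The last-observed-value rule substitutes the value in the right-hand column. The mixed model uses all earlier draws, but it deals with the missing later ones only if, given the observed data, missingness does not depend on the unseen values. Section 2.8.2 acknowledges the weakness of carrying values forward and adds multiple imputation, but it does so under the secondary endpoints.

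**5. How often would this happen?** The documents do not say. Their only withdrawal allowance is in the synopsis: "twenty-five subjects will be randomized to account for subjects who have been withdrawn early due to the current COVID-19 pandemic", and also for medical reasons unrelated to the study. That allows (25 − 18)/25 = 7/25 = 28%, but the figure pools causes and does not show how many fell under these two sentences.

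**6. Cost of keeping the draws.** At most 4 × 29 ml = 116 ml per affected subject, all already in the schedule.

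**The case against.** The strongest opposing case has four parts.

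- **The wording is loose rather than wrong.** The lead-in frames the list as stopping drug, so one clarifying line might settle it. That is fair, but the clarification is the change requested, and the drop-out language in Section 2.9.1 favours the stricter reading.
- **The plan already copes.** It excludes patients at higher risk of exacerbation, cites retention near 100% in several of the centre's studies, uses mixed models and randomises 25. These measures reduce how often the problem arises and use the earlier data. They do not supply the missing values, and extra subjects do not recover data from those who left.
- **Day 210 is not everything.** Section 2.8.1 allows the effect to appear by about six months, so the day 150 sample may already carry much of it. This stands: a late termination costs one draw and may change little.
- **Off-drug samples are hard to interpret.** A subject stopped after the day 30 infusion would give a day 210 sample 210 − 30 = 180 days after the last dose, perhaps after steroids. For a proof-of-concept biomarker trial, an on-treatment question is legitimate. This also stands. It is why an on-treatment summary should be shown alongside, but it does not remove the conflict with the stated intention-to-treat principle.

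A reader might go further and infer a specific loss of power. The documents do not support one. The plan's own figure reproduces: with a difference of 30, SD 20, 12 versus 6 and two-sided 0.05 (the plan does not state sidedness), the noncentrality is 30/(20 × √(1/12 + 1/6)) = 3.0 and t-test power is 0.80. But 25 are randomised; split about 17 to 8 (an assumption), the same inputs give 0.92. Any loss from there depends on event counts and carried-forward values that would have to be invented, and on a t-test rather than the planned mixed model. Nor do the documents support treating the 28% allowance as a termination rate under these rules, or claiming that the result is biased in a particular direction.

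**Conclusion.** The point holds as a gap in the protocol. Read as written, two sentences of Section 5.6.4 end participation, and nothing provides for endpoint sampling afterwards. For those subjects the intention-to-treat result rests on an earlier value or on a missing-at-random assumption that may fail, because the loss may be related to disease or treatment.

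The size per affected subject is one to four post-baseline samples. The size for the trial is unknown. The conclusion rests on taking the termination wording at face value and on the absence of any sampling provision in the sections listed. It should be corrected because correction is cheap, not because serious damage has been shown. Confidence is medium, mainly because of the inconsistent wording.

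**What to change.** Reword both sentences along these lines: the subject receives no further study drug but remains in the trial and, unless consent is withdrawn, gives the remaining scheduled endpoint samples on days 30, 90, 150 and 210. Every current trigger, including the IgG threshold, continues to stop drug.

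In Section 2.8.1, state that samples taken after drug is stopped enter the intention-to-treat mixed model. Record the date of last dose for each subject and show an on-treatment summary alongside.

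The cost is a protocol wording change and up to four already planned draws for each affected subject. The downside is that off-drug samples may understate the on-treatment effect. The gain is observed values in place of carried-forward or model-implied ones; the change is not offered as a way to restore power.

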5.6.5 Parameters to be Monitored

The following progress will be monitored throughout the course of the research to ensure the safety of subjects as well as the integrity and confidentiality of their data.

- An evaluation of the progress of the research study, including subject recruitment and retention, and an assessment of the timeliness and quality of the data.
- A review of collected data (including adverse events, unanticipated problems, and subject withdrawals) to determine whether there is a change to the anticipated benefit-to-risk assessment of study participation and whether the study should continue as originally designed, should be changed, or should be terminated.
- An assessment of external factors or relevant information (eg. Pertinent scientific literature reports or therapeutic development, results of related studies) that may have an impact on the safety and study participants or the ethics of the research study.
- A review of study procedures designed to protect the privacy of the research subjects and the confidentiality of their research data.

